	15.3	1.1	Trial Results	67
	15.3	1.2	Authorship	67
	15.3	1.3	Reproducible Research	67
16	Dat	a and	or Sample Sharing	67
17	' Trai	nslatio	onal Research Collection	68
	17.1	Con	sent for translational studies	68
18	B Pro	tocol	Amendments	68
19	Ref	erenc	es	70
20	Арр	endic	es	74

20.1	Appendix I - Translational Research Sample Collection	74
20.2 Aı	ppendix II – Safety Reporting Flowchart	74

General information

This document was constructed using the Comprehensive Clinical Trials Unit (CCTU) at UCL Protocol template Version 7. It describes the ENLIVEN-UK trial, sponsored by UCL and coordinated by CCTU.

It provides information about procedures for entering participants into the trial, and provides sufficient detail to enable: an understanding of the background, rationale, objectives, trial population, intervention, methods, statistical analyses, cost-effectiveness analyses, ethical considerations, dissemination plans and administration of the trial; replication of key aspects of trial methods and conduct; and appraisal of the trial's scientific and ethical rigour from the time of ethics approval through to dissemination of the results. The protocol should not be used as an aide-memoire or quide for the treatment of other patients. Every care has been taken in drafting this protocol, but corrections or amendments may be necessary. These will be circulated to registered investigators in the trial. Sites entering participants for the first time should confirm they have the correct version through a member of the trial team at CCTU. CCTU supports the commitment that its trials adhere to the SPIRIT guidelines. As such, the protocol template is based on an adaptation of the Medical Research Council CTU protocol template and the Standard Protocol Items: Recommendations for Interventional Trials (SPIRIT) 2013 Statement for protocols of clinical trials (1). The SPIRIT Statement Explanation and Elaboration document (2) can be referred to, or a member of CCTU Protocol Review Committee can be contacted for further detail about specific items.

Sponsor

University College London (UCL) is the trial sponsor and has delegated responsibility for the overall management of the ENLIVEN-UK trial to CCTU. Queries relating to UCL sponsorship of this trial should be addressed to the CCTU Director, CCTU at UCL, Institute of Clinical Trials & Methodology, [name] or via the Trial Team.

Funding

	persist on attempted correction. Clinical judgement will be made by the Investigator. 2. Infant too unstable for neurosurgical	
	intervention. (This is a clinical judgement made	

	by the responsible neurosurgeon, neonatologist and anaesthetic team). 3. Parents or carers unwilling to provide informed consent.	
Study Type	Phase III, multi-centre, assessor-blinded, randomised controlled interventional trial of NEL with temporising device (Intervention- Arm A) vs temporising device alone (control - Arm B) in preterm infants with PHVD, including an internal pilot study.	
	The primary outcome assessor will be blinded to the treatment allocation, as will the Trial Statistician and the Clinical Project Manager.	
	Treatment allocation will be in a 1:1 ratio using minimisation via www.sealedenvelope.com .	
Study setting	Paediatric neurosurgical units	
Date of First Enrolment	May 2024	
Target Sample Size	100	
Trial Duration	72 months	
Primary Objective	To establish the efficacy and safety of the addition of NEL to standard of care during temporising device insertion. It is hypothesised that the addition of NEL will be safe and will improve neurodevelopmental outcome at 2 years in children with severe IVH and PHVD.	
Primary Outcome(s)	To detect a 20-point (clinically significant) difference in the Cognitive Quotient (CQ) measured by the Bayley Scales of Infant and Toddler Development Fourth Edition (Bayley IV) at 2 years' corrected age (+/- 2 months) following addition of NEL to the standard of care.	
Key Secondary Outcomes	 Developmental Measures: a. Motor quotient (MQ) b. Language quotient (LQ) Other neurological and functional assessments conducted during the 2-year follow-up visit: a. Presence of seizures during the first 2 years and use of anticonvulsant medication at 2 years. b. Presence of cerebral palsy (+ accompanying Gross Motor Function Classification System (GMFCS) grade and deficit distribution map using the Classification of SCPE c. Assessment of hearing and vision (British Association of Perinatal Medicine classification) d. Parent report:	

	 Mortality up to 2 years corrected age. NEL & VP shunt related outcomes: a. Safety of NEL b. Further surgical procedures, including revision of the temporising drainage device (VAD or VSG), addition of a second temporising device, surgery for loculated or isolated ventricles, and revisions of the VP shunt, if implanted, until two years' corrected age. c. Requirement for VP shunt insertion at 6 months' corrected age.
	 5. Quality of life and health economic assessments: a. Health-Related Quality of Life (HRQoL) in children: assessed at 12-months and 2 years' corrected age b. HRQoL in primary caregiver: EuroQoL EQ-5D-5L assessed at baseline, 6 months, 12 months and 2 years' corrected age. c. Healthcare resource use costs: assessed at 3 -6-,12-, 18- months and 2 years' corrected age. d. Subsequent cost-effectiveness analysis & cost-benefit analysis of impact on carers based on responses to the EQ-5D-5L
Transitional Research Collections	 There will be 3 translational research collections: Collation of imaging: Immediate pre- and post-operative ultrasound scans and MRI scans performed until the child reaches 2 years of age will be collated in a centralised repository for future radiological biomarker analysis Collection of cerebrospinal fluid (CSF): CSF from the index surgery and, where applicable, permanent shunt insertion, and any unscheduled visits at the Neurosurgical Unit will be collected and stored for future biomarker analysis. Collection of blood: Blood from the index surgery and, where applicable, permanent shunt insertion, and any unscheduled visits at the Neurosurgical Unit will be collected and stored for future biomarker analysis.
Pilot Trial	An internal pilot trial will be conducted over the first 12 months of recruitment, beginning when the first centre opens. This pilot trial will have specific aims of assessing recruitment feasibility, barriers to recruitment and protocol adherence with a clear 'traffic light' progression

criteria. The progress of the trial will be reviewed by the
TSC and Funder against the traffic light progression
criteria The Independent Data Monitoring Committee
will also meet prior to progression beyond the pilot to
confirm there are no safety concerns.

Roles and responsibilities

These membership lists are correct at the time of writing; please see terms of reference documentation in the TMF for current lists.

Protocol contributors

i rotocoi continuatora		
Name	Affiliation	Role

QP	Qualified Person
R&D	Research and Development
REC	Research Ethics Committee
SAE	Serious Adverse Event
SAP	Statistical Analysis Plan
SCPE	Surveillance of Cerebral
	Palsy in Europe
SHINE	Bifida Hydrocephalus
	Information Networking
SOP	Standard Operating
	Procedure
TAPQOL	TNO-AZL Preschool
	Children's Quality of Life
TD	Temporising Device
TMF	Trial Master File
TMG	Trial Management Group
ToR	Terms of Reference
TSC	Trial Steering Committee
UCL	University College London
VAD	Ventricular Access Device
VSGS	Ventriculo-Subgaleal shunt
VP	Ventriculoperitoneal

Glossary

Term	Definition
Corrected age	Chronological age, minus the number of weeks the infant was born
Corrected age	before the time of 40 weeks gestational age.
Foreseeable SAE	Any AE that:
Foreseeable SAE	• results in death
	• is life threatening*
	• requires hospitalisation or prolongs existing
	hospitalisation**
	results in persistent or significant disability or incapacity
	• is a congenital anomaly or birth defect
	or is another important medical condition***
	AND
	•is listed in section 6.1.2 (Foreseeable Adverse Events)
	These events must be reported within 5 days of site becoming
	aware if there is no causal relationship to trial intervention (NEL).
	These events must be reported within 24 hours of site
	becoming aware if causally related to trial intervention (NEL).
Intraventricular	A bleed into the ventricles of the brain
Haemorrhage	
Neuroendoscopic	Procedure to 'washout' blood and blood products from the
Lavage	ventricles
Notifiable Adverse	Any AE that is listed in section 6.2 (Notifiable Adverse Events)
Event	
Post-haemorrhagic	Progressive ventricular enlargement and elevated intracranial
hydrocephalus	pressure following Intraventricular haemorrhage
Temporising Device	Device used to affect CSF drainage when an infant develops
3	PHVD. This will be either a VAD or VSGS.
Term equivalent Age	Age at which an infant would have been born if they had not been
	premature
Unforeseeable SAE	Any AE that:
	• results in death
	• is life threatening*
	requires hospitalisation or prolongs existing
	hospitalisation**
	results in persistent or significant disability or incapacity
	is a congenital anomaly or birth defect
	or is another important medical condition***
	AND
	•is not listed in section 6.1.2 (Foreseeable Adverse Events)
	These events must be reported within 24 hours of site
	becoming aware if causally related or unrelated to trial
	intervention (NEL).
Ventricular Access	Device used to affect CSF drainage by repeated aspiration when
Device (VAD)	an infant develops PHVD.
Ventricular	Procedure used to perform surgery within the ventricles of the
endoscopy	brain.
Ventriculo-Subgaleal	Device used to affect CSF drainage when an infant develops
shunt (VSGS)	PHVD.
SHUHL (VOUS)	FIIVD.

1 Background

1.1 Rationale

Around one in thirteen infants is born preterm in the United Kingdom. Despite major advances in survival, intraventricular haemorrhage (IVH) remains one of the most serious complications of preterm birth. In England, almost 500 children develop severe IVH annually (3). Over 50% of these progress to post-haemorrhagic ventricular dilatation (PHVD), where there is progressive enlargement of the ventricles, with distension of the periventricular white matter, raised intracranial pressure and injury to the developing brain. As well as pressure and distortion, the mechanisms of brain injury in PHVD include pro-inflammatory cytokines and free radicals from iron and hypoxanthine persisting in the ventricles for months (4). In childhood, PHVD is associated with a very high rate of cognitive disability and cerebral palsy (CP) (5). IVH and PHVD are the most common cause of neurological disability in preterm infants and have been shown to be the most significant predictors of cognitive disability (3,6,7). Optimising early and effective management in the neonatal period is therefore important to improving long-term cognitive and functional outcomes, both of which are extremely important to families of these children (8).

Current management involves drainage of cerebrospinal fluid (CSF) only (9). Although there is no established consensus on the management algorithm, most UK centres follow a stepwise approach which involves the insertion of an initial temporising device (a ventricular access device (VAD) or ventriculo-subgaleal shunt (VSGS)) when the infant develops PHVD. In up to 75% of these children, permanent CSF diversion via a ventriculoperitoneal (VP) shunt is required, which usually occurs around term-equivalent age. Despite this rational approach, there is still significant morbidity with high rates of shunt dysfunction requiring revision surgery (10).

Optimising long-term cognitive and functional outcomes is important in this patient group as it has been shown to be a priority for families of children with hydrocephalus (8,11). Despite timely intervention, the burden of poor neurodevelopmental outcomes is worse in PHVD compared to other forms of infant hydrocephalus (12). The increased risk of poor outcomes carries important economic implications, from increased time in intensive care through higher requirements for allied health professional support, to long-term special education needs in 60%. These increased needs may reduce family employment prospects (13).

This research is therefore important because severe cognitive disability deprives the child of education, independence and employment, and places unusually heavy demands on the rest of the family and society as well as healthcare resources.

1.1.1 Explanation for choice of comparators

Several interventions for PHVD have been tested in randomised trials and non-randomised studies at various stages of the treatment pathway. Although in the past, treatment was only started once the ventricles were large enough to raise intracranial pressure and cause symptoms with overt neurological deterioration, recent studies have suggested that earlier treatment, based on standardised ultrasound measurements of ventricular size, is beneficial (14,15). Across the UK, the majority of paediatric neurosurgical units have taken a ventricular size of 4mm above the 97th centile as the treatment threshold.

The use of acetazolamide and furosemide to reduce CSF production resulted in increased death, disability or impairment and probably increased requirement for a VP shunt (16). Repeated taps, lumbar punctures and intraventricular streptokinase to remove clot from CSF pathways also did not improve outcome (17,18).

The DRIFT (Drainage, Irrigation, Fibrinolysis Trial) study was the first trial to demonstrate a significant reduction in the proportion of children with severe cognitive disability or death at follow-up at two and ten years (13,19,20). The improved cognition at ten years was equivalent

to a two-year developmental improvement. This suggested that effective washout of blood from the CSF may limit the extent of brain injury. DRIFT involves the insertion of two catheters into the ventricles of a premature infants: irrigating fluid flows in through one and out through the other. The irrigation is continued for about five days, during which very close and specialist monitoring of fluid flow and intracranial pressure is required. DRIFT also requires the use of fibrinolytic agents, and a proportion of babies had secondary bleeds in the ventricles following treatment. The DRIFT technique requires specialist and dedicated expertise over a long period of time, and is difficult to implement, teach and disseminate. Development of techniques that enable easier lavage of intraventricular blood, ideally contained within a single brief surgical procedure, is required.

In the last five years, neuroendoscopic lavage (NEL) has been suggested as a promising treatment option. It is a 30-minute adjunct to the surgical procedure of inserting the temporising device into the enlarged ventricles. NEL washes out blood, clot and its breakdown products as well as debris from the CSF within the ventricles (Figure 1). Unlike DRIFT, NEL does not require injection of a fibrinolytic agent, reducing the risk of secondary haemorrhage. By washing out the blood, NEL may also reduce scarring within the CSF flow pathways, improve CSF circulation and reduce the risk of requiring permanent CSF drainage with a VP shunt. Retrospective evaluations from Europe have shown promising results with the procedure showing safety, reductions in permanent VP shunt insertion and revision rates and favourable neurodevelopmental outcome, although none were prospective comparative trials (21-25). Although not part of the standard of care in the UK, paediatric neurosurgeons carry out endoscopic procedures and NEL for other indications in babies, older children and adults, and are therefore comfortable and competent to perform the procedure.

Figure 1 - Example of cranial ultrasound scan (a) before and (b) after NEL. (a) Ultrasound before NEL showing dilated lateral ventricle (white arrow showing left ventricular index measurement) and extensive clot (yellow asterisk) within them. (b) Ultrasound after NEL showing a decompressed ventricular system with reduced clot burden.

Over the last 3 years, the ENLIVEN (Endoscopic Lavage after Intraventricular Haemorrhage in Neonates) pilot study at Great Ormond Street Hospital (GOSH) has been randomly assigning preterm infants with PHVD to VSGS with NEL or VSGS alone (26). Between January 2018 and January 2022, 17 infants have been enrolled in this single centre pilot study. This represents two thirds of the admissions to the service for treatment of PHVD, establishing that recruitment is feasible and that parents are willing to enrol their child. NEL was carried out with an endoscope on the side of the greater blood load. The study was powered to detect a reduction in the need for VP shunt insertion at 6 months. To date we have seen no difference in the primary outcome in this small number of patients. Infants who underwent lavage were less likely to require tapping or revision of their VSG shunt, suggesting that the overall reduction in the amount of blood and debris in the CSF by the irrigation reduced the risk of VSG shunt blockage. The median body weight at NEL in this patient group was 886g; although this was lower than in the published studies described above, there have been no safety concerns.

The above evidence makes a compelling case to undertake a large multi-centre randomised controlled trial of NEL in the UK to assess efficacy and safety.

1.2 Objectives

The objective of this study is to establish the efficacy and safety of the addition of NEL to standard care during temporising device insertion. It is hypothesised that the addition of NEL will be safe and will improve neurodevelopmental outcomes at 2 years in children with severe IVH and PHVD.

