The intervention being evaluated in this randomised trial, NEL will be carried out in addition to insertion of a temporising device (Arm A - Intervention). In our experience and in published studies, the additional risks of endoscopic lavage are low, and occur in less than 5% of cases

(21-25). The risks relate to standard neuro-endoscopic surgery and are expected to be lower than the risks of DRIFT. These include infection, further haemorrhage within the ventricles, haemorrhage related to ventricular decompression, seizures, CSF leak, electrolyte disturbance and a <1% risk of brain injury (21-25). These risks are not expected to be significantly higher than insertion of a temporising device alone. In theory the risk of electrolyte disturbance and seizures, related to the presence of lavage fluid within the ventricles, is slightly higher than with insertion of a temporizing device. This will be mitigated by use of warm Ringer lactate solution or artificial CSF, and by monitoring of serum electrolytes post-lavage. These infants are routinely cared for within a neonatal intensive care unit environment and close care and supervision is routine.

Several published studies have suggested that the requirement for permanent CSF diversion through a ventricular peritoneal shunt is reduced after lavage compared to insertion of a temporising device alone (22,24,25). This is a potential additional advantage of NEL that will be evaluated as an exploratory outcome.

The risks associated with NEL will be mitigated by ensuring that patient recruitment will only take place in established paediatric neurosurgical units and will be undertaken by paediatric neurosurgeons who routinely perform a range of neuro-endoscopic procedures. Each paediatric neurosurgical unit is affiliated with a neonatal unit to ensure appropriate neonatal care. A number of meetings have taken place to discuss the technical details of the irrigation procedure, and a surgical consensus statement has been published (28). In addition, a meeting with world experts in endoscopic lavage in this population is planned before commencement of recruitment to enable a wider discussion and sharing of operative nuances, experience and knowledge.

2 Selection of Sites/Investigators

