8.1 Sample Size

The sample size required for the ENLIVEN-UK trial utilised individual patient data from the DRIFT trial, which showed that the distribution of cognitive quotient (CQ) in the 'standard treatment' arm at 2 years' corrected age was approximately uniform in the 0—100 interval with a median of approximately 50 (Figure 2a) (19). The distribution in the DRIFT arm was more skewed, with a median of approximately 70 (Figure 2a) (19). This was evident at 10 years, with a median difference of 25.6 (46.7 in the control arm vs 72.3 in the DRIFT arm) (13). We hypothesise that, mechanistically, NEL would achieve the same effect as DRIFT. We therefore estimate a median difference of 20 points between our treatment arms. A difference of 20 points is considered clinically significant, representing approximately a 5-month difference in developmental age at 2 years and a 2-year difference at 10 years. That this was also considered a significant and valuable difference to parents, as confirmed by a focus group led by our parent co-applicant [name].

To reflect results shown in DRIFT, the distribution of CQ in the control arm was modelled using a Beta(1,1) distribution, equivalent to the uniform distribution. The distribution in the experimental arm was modelled to be a Beta(10, 4.25). Both distributions were multiplied by 100 to reflect the 0—100 CQ scale (Figure 2b). Using simulations performed in R with 1000 replications, we established that 45 patients in each arm, totalling 90 patients, would provide 90% power to detect the hypothesised treatment effect, based on a Wilcoxon-test with two-sided alpha of 5%. To account for a 10% loss to follow-up and other methodological challenges during the study, we aim to recruit 100 patients in this study, 50 in each arm.

[figure not shown]

Figure 2: (a) Developmental quotient (old name for cognitive quotient on Bayley II) distributions in control (TD) and intervention (DRIFT) arms of the DRIFT trial. (b) Estimated distributions of cognitive quotient scores at 2 years in the control (TD) and intervention (NEL + TD) arms of the ENLIVEN-UK Study.

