8.3.7 Additional Analyses – Secondary

The secondary outcome measures are listed in Section 5.1.2. All measures will be analysed using methods appropriate to their data structure. As a general principle summary statistics

for continuous variables used will be mean, median, SD, lower quartile, upper quartile and reported appropriately according to distribution. Summary statistics for binary and categorical variables will be n (%).

Notable analysis points:

- Motor quotient and Language quotient will use the same approach as the primary outcome measure.
- Mortality up to 2 years will be analysed using survival analysis techniques the Log-Rank test will be used to test for a difference and non-proportional hazards will be assessed to decide the most appropriate modelling technique, displayed using a Kaplan-Meier plot.
- Graphical representations of the harm profile will be guided by the Phillips et al. Publication (32)

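### The primary objective is to establish that NEL is safe, but 50 per arm and a log-rank test for a mortality difference can only estimate safety, and imprecisely

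*Protocol*

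**What the plan says.** The structured trial summary gives as the primary objective: "To establish the efficacy and safety of the addition of NEL to standard of care during temporising device insertion". Section 1.2 repeats this: "The objective of this study is to establish the efficacy and safety of the addition of NEL to standard care". It continues: "It is hypothesised that the addition of NEL will be safe". Neither place says what excess of harm would still count as safe.

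Section 8.1 justifies the sample size on CQ at 2 years only: "45 patients in each arm, totalling 90 patients, would provide 90% power to detect the hypothesised treatment effect". After allowing for losses, "we aim to recruit 100 patients in this study, 50 in each arm". No safety outcome enters that calculation.

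Section 5.1.2 lists mortality as one secondary outcome and the number of adverse events as another. For mortality, section 8.3.7 says the "Log-Rank test will be used to test for a difference and non-proportional hazards will be assessed to decide the most appropriate modelling technique". No sidedness or alpha is given for this test; section 8.3.5 sets a two-sided 5% level for the CQ analysis. Adverse events get no named test. They fall under a general statement about appropriate methods, with summary statistics and graphs of the harm profile.

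Section 1.4 puts the complications of the temporising device below 5% and says of NEL that "the additional risks of endoscopic lavage are low, and occur in less than 5% of cases". It does not expect the risks with NEL to be materially above those of the device alone.

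**The concern.** Saying that an added procedure is safe means that it brings no important excess of harm over control. Showing this needs either a stated margin or an interval narrow enough to exclude an excess that matters. A test for a difference does neither: a non-significant result fits both no harm and harm too small for the trial to detect.

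Section 8.3.5 fixes an effect measure and a 95% interval for CQ. For mortality no effect measure is fixed, because the model depends on a look at proportional hazards. With few deaths that look will be uninformative, so the form of the main safety estimate would be decided after the data are seen, on weak evidence.

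At stake is the safety half of the primary objective of a phase III trial in very fragile infants, which the protocol hopes will support use of NEL across the UK. If the report echoes the objective's verb, it will claim more than the data can carry.

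**Working it through.** **Inputs from the protocol.** 50 infants per arm, 1:1 (8.1); log-rank test for a mortality difference (8.3.7).

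**Assumptions.** The protocol gives no mortality rate, so control mortality p at 2 years is taken as 5% to 20%. A two-sided 5% level is carried over from section 8.3.5. No loss to follow-up is applied, which favours the trial.

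**1. The plan's own figure.** Simulating the Wilcoxon test with 45 per arm, 100 × Beta(1,1) against 100 × Beta(10, 4.25), gives power of 91.2% (asymptotic) and 91.3% (exact) against the stated 90%. Then 90 / (1 − 0.10) = 100. The CQ sample size reproduces; the question is what the same 100 infants can show about harm.

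**2. Log-rank power when 2-year mortality doubles from p to 2p.** Expected deaths are D = 50(p + 2p), the hazard ratio is HR = ln(1 − 2p) / ln(1 − p), and Schoenfeld power is Φ(½√D · ln HR − 1.96). For 10% vs 20%: D = 15, HR = 2.12, ½√15 × 0.750 = 1.453, and Φ(1.453 − 1.96) = Φ(−0.507) = 31%. A simulated log-rank test (exponential times, censoring at 2 years, 6,000 replications) is set beside it.

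| Control vs NEL | Deaths expected | HR | Schoenfeld power | Simulated power | Missed (simulated) |
|---|---|---|---|---|---|
| 5% vs 10% | 7.5 | 2.05 | 16.5% | 14% | 86% |
| 10% vs 20% | 15 | 2.12 | 31% | 28% | 72% |
| 15% vs 30% | 22.5 | 2.19 | 46% | 44% | 56% |
| 20% vs 40% | 30 | 2.29 | 62% | 60% | 40% |

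If doubling is read instead as a hazard ratio of exactly 2, Schoenfeld power over the same control risks is 15%, 26%, 36% and 45%, so 85% to 55% are missed.

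**3. Deaths needed.** For HR = 2 with 80% power: 4(1.96 + 0.842)² / (ln 2)² = 4 × 7.85 / 0.480, or 66 deaths (71 by Freedman's formula). About 7 to 28 would be expected over the control risks in step 2.

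**4. What the intervals could exclude.** This step needs no assumed mortality rate, only an observed count.

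- 5/50 in each arm: the Wilson limits for 10% are 4.3% and 21.4%. The Newcombe half-width is √[(0.100 − 0.043)² + (0.214 − 0.100)²] = 0.127, so the risk difference runs from about −13 to +13 points.
- 5/50 control vs 10/50 NEL: Fisher p = 0.26, with a 95% interval of −4 to +24 points.
- 0/50 events in one arm: the exact two-sided 95% upper limit is 1 − 0.025^(1/50) = 7.1%, above the 5% that section 1.4 quotes.

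**5. What a formal safety claim would take (illustrative margins; the protocol states none).** With 5% risk in both arms, one-sided 2.5% and 80% power, a 5-point margin needs 7.85 × 2 × 0.05 × 0.95 / 0.05², or 299 per arm. A 10-point margin needs 75 per arm. Both exceed 50.

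**The case against.** Sizing a trial on its primary efficacy outcome and treating safety as secondary is ordinary design. Section 8.3.1 calls the statistical section version 0.1 of the SAP, so much of the detail of safety reporting belongs in the later document. Safety is also not left to the log-rank test: there are adverse event counts, summary statistics, harm graphs, prompt reporting of every death to the IDMC, and IDMC review of unblinded benefit and risk. Section 1.1.1 already describes the aim as assessing efficacy and safety.

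Most of that stands, and it rules out three stronger readings that a reader might infer.

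- *That the trial will conclude safety from a non-significant p-value.* No section says so, and descriptive reporting is planned alongside the test.
- *That the planned safety test misses doubled complications up to 94% of the time.* The log-rank test covers mortality only, and no test is named for complications. The 94% comes from Fisher's test at 5% vs 10%; a pooled z test gives about 84%. The 5% vs 10% contrast itself comes from adding two upper bounds in section 1.4, not from a rate the protocol states.
- *That a doubling of mortality is missed at least 55% of the time.* That depends on the assumed control risk and on what is doubled. At 20% vs 40% the figure is about 40%.

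The two-sided level for the log-rank test is likewise an assumption.

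What the defence does not remove is the objective itself. Its wording is protocol text, and no SAP can make 50 per arm establish safety. Counts and graphs describe, and the IDMC protects participants during the trial; neither supplies a criterion for safe. Attributed causality cannot replace a comparison between arms either, because section 6.1.2.1 treats all foreseeable SAEs in the control arm as unrelated to NEL. Leaving the mortality effect model to a data-dependent check is also stated in the protocol, so it is not merely an omission.

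**Conclusion.** The concern holds in a limited form. The primary objective and its hypothesis claim more about safety than the design can deliver, and the one inferential method named for a safety outcome does not fix an effect measure. With 50 per arm, a doubling of 2-year mortality would be missed about 86% of the time at 5% control mortality, falling to about 40% at 20%. Equal counts of 5/50 would still leave an excess of about 13 points within the 95% interval.

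The power figures rest on assumed control mortality, a two-sided 5% level and complete follow-up. The interval figures rest only on 50 per arm and the illustrated counts. Power is below 80% throughout the assumed range.

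Severity is minor: the CQ sample size and analysis are untouched, and the remedy is wording plus one pre-specified estimate.

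**What to change.** 1. In the structured summary and section 1.2, reword the objective so that the trial establishes efficacy and assesses (or estimates) safety. Drop the statement that NEL will be safe as a hypothesis to be confirmed.
2. In section 8.3.7, fix the mortality effect measure as the Kaplan-Meier risk difference, NEL minus control, at 2 years' corrected age with its 95% confidence interval, whatever the proportional-hazards assessment shows. Keep the log-rank p-value as supportive and state whether it is two-sided.
3. Say in section 8.3.7 that safety is interpreted from the interval, especially its upper limit, and that a non-significant p-value is not evidence of safety.

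Interval methods for individual complications can be left to the SAP.

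The cost is an edit to three places and one estimate from data already collected, with no extra patients, visits or procedures. The downside is a less favourable safety claim in the final report.
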